# 2.2 Secondary Objectives (if applicable)

NA

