#### CONFIDENTIAL

conditions such as time of day and other risk factors. For the OGTT, samples are then collected at 30, 60, 90, and 120 minutes post glucose ingestion. We will compute the Matsuda whole body Index of Insulin Sensitivity (ISI) as follows and will be used at the insulin resistance (IR) variable:

 $ISI = \frac{10,000}{\sqrt{[fasting glucose x fasting insulin] x [mean glucose x mean insulin during OGTT]}}$ 

Baseline bloods obtained at time 0 will also be analyzed for measuring HgbA1C and C-reactive protein (CRP). In addition, we will use baseline bloods to estimate levels of hydrogen peroxide as a marker of ROS. None of these blood biomarkers will be used as an inclusion/exclusion criterion.

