# 9.3 Description of Statistical Methods

A weighted paired sample *t*-test will be used to assess whether each outcome changed from baseline to follow-up as a result of the exercise intervention. Weighted analysis of covariance (ANCOVA) will be used to compare the time points in terms of the change in each outcome. The change in each outcome from baseline to follow-up will be the dependent variable and the ANCOVA model will include the matching factors (age, baseline MNSI) and the measure of general activity level as numeric covariates and the binary indicator of intervention as a classification factor. The secondary objective is to assess the extent to which exercise induced improvements in DTI outcomes are mediated or explained by reduction in ROS. After testing the effect of the intervention on the change in DTI and the correlation between changes in DTI and ROS, an incomplete causal pathway meditational analysis will be conducted using the method of Baron and Kenny[63] with a bootstrap based test of the indirect (mediation) effect of ROS. The exploratory objective to identify baseline factors (e.g., age, MNSI, general activity) predictive of improvement, represented as the baseline to follow-up change in each outcome, will be addressed using linear regression and bivariate correlations. This analysis will be stratified by intervention and then conducted using data from both intervention groups combined. In each case, the assessment of compliance will be included as a weighting factor.

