# 9.3.2 Analysis of the Primary Efficacy Endpoint(s)

A matched-pairs Wilcoxon signed rank test will be applied to the within-subject change in each outcome among subjects demonstrating full compliance with the exercise program. Additionally, weighted analysis of covariance (ANCOVA) will be used to test the change in each outcome adjusting for the measured level of compliance using data from all subjects. The values of each outcome at

CONFIDENTIAL

baseline and follow-up for all subjects will be the dependent variable and the ANCOVA model will include time (baseline versus follow-up) as the within-subject factor of interest covariates, the measure of compliance as numeric covariate and an anonymized subject ID as a classification factor so that the comparison of times will be based on their within-subject difference. The secondary objective is to assess the extent to which exercise induced improvements in DTI outcomes are can be at least partially explained by reduction in ROS will be addressed using linear regression, The baseline to follow-up change in each outcome will be the dependent variable and the model will include the measure of compliance as a numeric factor and the within-subject change in ROS as the numeric factor of interest. A second regression will be conducted with baseline factors (e.g., age, MNSI, general activity) added to the model in order to identify factors predictive of improvement in each outcome.

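### The ROS-to-DTI objective has two unreconciled analyses, and as scheduled ROS has no control-phase change, so exercise-versus-control mediation cannot be estimated

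*Combined protocol and SAP*

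**What the plan says.** All references are to the combined protocol and SAP.

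- **Section 9.3** names a secondary objective, ROS reduction as the explanation of DTI improvement. The order of work is "After testing the effect of the intervention on the change in DTI and the correlation between changes in DTI and ROS", after which "an incomplete causal pathway meditational analysis will be conducted using the method of Baron and Kenny", "with a bootstrap based test of the indirect (mediation) effect of ROS". The ANCOVA in the same paragraph carries "the binary indicator of intervention as a classification factor", and the paragraph ends: "In each case, the assessment of compliance will be included as a weighting factor".
- **Section 9.3.2**, headed as the primary efficacy analysis, repeats the objective but says that what "can be at least partially explained by reduction in ROS will be addressed using linear regression". The dependent variable becomes the change in each outcome, and compliance enters as a numeric covariate. The model has no intervention term, no indirect effect and no bootstrap.
- **Sections 2.2, 3.2.2 and 9.3.3** (secondary objectives, endpoints and their analysis) are marked NA.
- **Section 6.2.1** gives the source of the ROS measurement: "we will use baseline bloods to estimate levels of hydrogen peroxide as a marker of ROS". Baseline there means the time-0 sample of the glucose tolerance test (OGTT), not the study baseline.
- **Attachment A** shows OGTT and bloodwork at Weeks 1 and 18, MRI at Weeks 1, 5 and 18, and exercise in Weeks 7 to 16. Sections 3.2.1 and 6.2.1 likewise describe these measurements as made before and after the intervention.
- **Sections 2.1 and 9.1** make the exercise-versus-control comparison of change, ROS included, the primary objective. Hypothesis 1b is that exercise lowers ROS.

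**The concern.** Two things are at stake. First, one objective has two analyses that differ in outcome, in test and in the role of compliance. They can give different answers, and nothing says which one counts, so the choice could be made after the results are seen. The objective is also missing from every section where a reader would look for it.

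Second, Section 9.3 plans a mediation conclusion about exercise. A mediation effect is the effect of the intervention on the mediator multiplied by the effect of the mediator on the outcome. The first factor needs a ROS change with exercise and a ROS change without it. If ROS is sampled only at the start and end of the whole study, the second of these does not exist, and a general change over time would be credited to exercise.

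**Working it through.** **1. The plan's own power figure.** Section 9.4 gives detectable changes of 10% to 18% of the baseline mean at 80% power, n = 40, two-sided 5%. A paired t calculation from the Table 4 exercise SDs and Table 3 baseline means gives 17.7% for BOLD (SD 1.26, mean 3.24), 15.5% for MNSI (1.78, 5.2) and 14.2% for PCr (12.85, 41.16). The upper end reproduces. The lower end cannot be checked, because the control columns of Table 3 are not legible in the text available. No power figure is given for ROS, DTI or an indirect effect, so there is none to reproduce for this point.

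**2. The two analyses side by side.**

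| | Section 9.3 | Section 9.3.2 |
|---|---|---|
| Outcome | DTI change | change in each outcome |
| Intervention contrast | tested first | none |
| Quantity tested | indirect effect, a × b | slope on ROS change |
| Test | bootstrap | regression |
| Compliance | weight | covariate |

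**3. Is path a estimable?** Path a is the coefficient of intervention in: ROS change = constant + a × intervention.
- As scheduled: 40 ROS changes (Week 1 to Week 18), with the indicator equal to 1 for everyone. The matrix [1, intervention] has rank 1, so a cannot be separated from the constant.
- With a further ROS sample at the end of the control phase: 80 changes (40 control, 40 exercise), rank 2, and a is estimable.

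DTI has the control-phase change (Week 1 to Week 5) in Attachment A and Section 1.2. Section 9.3.1 says that imaging happens only twice, which would remove that one too.

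**4. The pre/post substitute.** If time replaces the intervention, path a becomes the mean ROS change from Week 1 to Week 18. That interval is 18 − 1 = 17 weeks, of which 10 are exercise weeks. Its mean is (drift unrelated to exercise) + (exercise effect), and the data show only the sum.

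Simulation: 3,000 trials of n = 40. ROS change has mean d and SD 1, and its correlation with DTI change is r. A trial is declared positive if the mean ROS change and the slope are both significant at 5%, a stand-in for the bootstrap. The values of d and r are assumptions, because the documents give none.

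| Drift d (SD of ROS change) | r = 0.3 | r = 0.5 |
|---|---|---|
| 0 | 2% | 5% |
| 0.3 | 22% | 43% |
| 0.5 | 41% | 80% |
| 0.8 | 46% | 92% |

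A true exercise effect of size d would give exactly the same rates, so the test cannot tell the two apart.

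**5. Can the two planned analyses disagree?** The slope test uses only deviations from the mean, so its rejection rate does not depend on d. It is also at least the joint rate. At r = 0.5 it is therefore about 92% or more, from the last row. With no mean ROS change (d = 0), the joint test is positive in only 5%. In that case the Section 9.3.2 approach would usually report that ROS explains the change, and the indirect-effect test would usually report that it does not.

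**6. Sensitivity of a simple correlation.** By Fisher's z, the correlation detectable with 80% power is tanh[(1.960 + 0.842)/√(40 − 3)] = tanh(0.461) = 0.43. This is context for whichever analysis is kept. It does not measure the defect, because it would be the same under a consistent plan.

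**The case against.** **The schedule may not be the whole story.** The Attachments page says that the attachments are not part of the protocol. The contents list and Section 4.7.2 refer to a post-non-exercise phase visit, but no section in the available body describes it. Section 1.2 uses pre-intervention for the second imaging time point, distinct from baseline. The pre-intervention OGTT in Section 6.2.1 could therefore mean a draw at the end of the control phase, in addition to the baseline-visit OGTT of Section 6.4.1.2. This stands as a reason to ask: the missing sample is probable, not proven. If blood is drawn there, Attachment A needs correcting and the estimability part falls. The conflict between Sections 9.3 and 9.3.2 and the NA entries remain.

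**The two analyses overlap.** The Section 9.3.2 regression is close to the second path of Baron-Kenny, and Section 9.3 itself lists the correlation of changes as a preliminary step. That is fair, but the model, the test and the use of compliance still differ, and neither analysis is said to govern.

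**A reader might infer that no mediation analysis can be run at all.** The documents do not support that. A two-occasion analysis with time as the exposure can be computed from Weeks 1 and 18, and Section 9.3.2 already uses time as a within-subject factor. What cannot be estimated is the contrast with the control phase.

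**A reader might also infer that the result would be presented as proof of mechanism.** No passage says so. The wording is hedged: the pathway is called incomplete and the explanation partial.

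**Conclusion.** The point holds in this form. The secondary objective appears only in the methods text, with two analyses that are not reconciled, while three sections mark secondary objectives, endpoints and their analysis as NA. On the Attachment A schedule, which agrees with Sections 3.2.1 and 6.2.1, ROS has no control-phase change, so the exercise-versus-control mediation of Section 9.3 cannot be estimated. The computable pre/post version confounds exercise with time. The 22% to 80% rate of misattributed mediation depends on assumed drift of 0.3 to 0.5 SD and change correlations of 0.3 to 0.5, and on a joint-significance test without compliance weights. It illustrates the risk and is not a forecast.

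The same gap reaches further than the secondary objective: the primary exercise-versus-control comparison of ROS (Sections 2.1 and 9.1, Hypothesis 1b) has no control-phase ROS change either. All of this rests on no blood being drawn at the post-non-exercise visit, which the sponsor must confirm.

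**What to change.** 1. Confirm whether blood for ROS is drawn at the post-non-exercise visit, and make the text and Attachment A agree. If it is drawn, the contrast in Section 9.3 is estimable, and what remains is to list the objective and choose one analysis.
2. If it is not drawn, list the objective in Section 2.2, align Sections 3.2.2 and 9.3.3, keep one analysis and delete the other. Recommended: for each DTI measure, regress the Week 1 to Week 18 change on the ROS change over the same interval and on the participant's mean ROS, centred. Use a percentile bootstrap over participants for the interval on the ROS-change slope.
3. State one handling of compliance, either weight or covariate.
4. Report the result as a within-person association, not as mediation, and state that the interval includes the 4-week non-exercise period.
5. Restate the ROS hypothesis (1b, and the ROS part of Sections 2.1 and 9.1) as a pre/post change.

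The cost is wording only, with no new procedures. The price is a weaker causal claim: the trial could say that ROS and DTI changed together, not that exercise acted on the nerve through ROS.

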## 9.3.1 General Approach

In this longitudinal, single-center study we will recruit 40 T2DM patients. Each participant will be imaged two times: upon enrollment (visit 1) and after completion of the 10 week exercise program (visit 3).

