# 1.2 Rationale

Hyperglycemia is an important factor in the development of DPN. However, the pathophysiological processes through which hyperglycemia causes DPN are not fully understood. Furthermore, large clinical studies (ACCORD [27], ADVANCE [28], VADT [29]) have shown that good glucose control is insufficient to reduce the occurrence of foot complications, including DPN and diabetic foot ulcers. There are no Food and Drug Administration (FDA)-approved treatment options that target the underlying pathogenesis of DPN [19, 30]. Therefore, it is important to establish strategies to delay or reverse the effects of DPN.

We hypothesize that DPN patients who undergo 10 weeks of exercise will show improved peripheral nerve integrity and function, and that exercise will improve the structure, local metabolic, and MV functions of skeletal muscle. A major obstacle to assessing how DPN affects skeletal muscle and peripheral nerves is the lack of sensitive, objective, and reproducible tests to detect small changes in muscle and nerve functions [10]. Multinuclear-MRI can bring new insights into how DPN affects skeletal muscle (31P)-MRI techniques that can reliably assess skeletal muscle metabolic function [34, 35], as well as rapid

CONFIDENTIAL

This material is the property of the NYU School of Medicine and Langone Medical Center. Do not disclose or use except as authorized in writing by the study sponsor

techniques to quantify blood oxygenation level dependent (BOLD)-MRI signals, sensitive to MV function [36-38] and its adaptations after exercise interventions [39]. In addition, we will use diffusion tensor imaging (DTI), a powerful MRI technique, to quantitatively assess neuronal integrity and detect nerve injury and monitor reinnervation [40-46]. The use of DTI will allow us to non-invasively assess peripheral nerve adaptations after exercise intervention. Finally, we will use IDEAL-MRI to quantify levels of intramuscular adipose tissue (IMAT), which are elevated in DPN [47-50]. We will prescribe a 10-week exercise program, with both aerobic and resistance components [14, 24], to 40 DPN patients who will receive personal supervision from health professionals. We will acquire multinuclear-MRI data at three time points: 1) baseline, 2) pre-intervention and 3) post-intervention. We will measure plasma levels of reactive oxidative species (ROS) as markers of oxidative stress.

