# 3 Study Design and Endpoints

# 3.1 Description of Study Design

This single-center, longitudinal design study uses multinuclear-MRI to evaluate the mechanistic effects of exercise on skeletal muscle function and peripheral nerve integrity in patients with DPN, and to determine whether exercise can reverse DPN symptoms. Forty DPN patients will be enrolled and be prescribed a 10-week exercise program following a 4-week non-exercise period. The exercise program will comprise aerobic and resistance components; a moderate level of intensity will be calculated based on results from a maximal graded exercise test (VO2R) conducted prior to the intervention. Multinuclear-MRI data will be acquired at baseline, as well as before and after the intervention that can provide mechanistic insight into the adaptations in lower leg muscle function and peripheral nerve integrity of patients with DPN, and their role in improving DPN symptoms.

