# 4.5 Duration of Study Participation

Participants will be enrolled for a minimum of 10 weeks. We anticipate that some participants will be enrolled for greater than 10 weeks due to challenges associated with scheduling study procedures (limited availability on the MRI scanners). Additionally, we are allowing a one-week grace period during the intervention for patients who express pain/soreness due to the exercise regimen, or for other circumstances (i.e., planned vacation).

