# 9 Statistical Considerations

# 9.1 Statistical and Analytical Plans

The primary objective is to assess and compare the interventions (exercise versus control phase in the same individual) in terms of the baseline to follow-up change in the following outcomes: 1) DTI, plasma ROS level, and the MNSI assessment of DPN symptoms (Aim 1); and 2) leg mitochondrial function, oxidative capacity (31P-MRI), peak MV response (BOLD-MRI), the proportion of fat-free muscle (IDEAL-MRI) and leg muscle strength (Aim 2).

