## 12.3 Participant Reimbursements or Payments

Each participant will be offered \$500 upon completion of the 10-week supervised exercise intervention. They will also receive a clincard (similar to a debit/credit card) of \$50 for undergoing each MRI scan (two in total) and up to \$20 reimbursement for travel to our facilities.

If attendance during the exercise phase drops below 80%, reimbursement will be prorated based on the number of sessions completed. Participants will receive \$17 per session.

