# Attachments

These documents are relevant to the protocol, but they are not considered part of the protocol. They are stored and modified separately. As such, modifications to these documents do not require protocol amendments.

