# Attachment A

# Schedule of Events

Activity	Week 0	Week 1	Week 2	Week 3	Week 4	Week 5	Week 6	Week 7	Week 8	Week 9
Consent		Х								
MNSI	Х	Х								
Medical History	Х									
Height/Weight		Х					Х			
OGTT		Х								
Biweekly Health Assessment				х		Х				
VO 2 R Assessment							Х			
Plantar flexion training		Х								
Bloodwork		Х								
Actigraph**		Х	Х					Х	Х	
MRI		Х				Х				
Aerobic exercise								Х	Х	Х
Resistance exercise								Х	Х	Х
PROMIS								Х		
Calf muscle performance								Х		
9-item physical performance test								Х	Х	Х
Blood Pressure (BP)								Х	Х	Х

\*\*Actigraph to be worn for at least one week.

CONFIDENTIAL This material is the property of the NYU School of Medicine and Langone Medical Center. Do not disclose or use except as authorized in writing by the study sponsor Drug/Device Template Version: 13 JUN 2016

Page 2

# Attachment A Schedule of Events Cont....

Activity	Week 10	Week 11	Week 12	Week 13	Week 14	Week 15	Week 16	Week 17	Week 18
Consent									
MNSI									Х
Medical History									
Height/Weight								Х	
OGTT									Х
Biweekly Health Assessment									
VO 2 R Assessment								Х	
Plantar flexion training									
Bloodwork									Х
Actigraph						Х	Х		
MRI									Х
Aerobic exercise	Х	X	х	Х	х	Х	х		
Resistance exercise	Х	х	х	Х	х	Х	х		
PROMIS							х		
Calf muscle performance							х		
9-item physical performance test	X	X	X	X	X	х	X		
Blood Pressure (BP)	X	Х	Х	Х	Х	Х	х

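### Sections 9.3.1 and 12.3 give two MRI scans where 1.2, 3.1 and Attachment A give three; if 9.3.1 is followed, exercise versus control cannot be estimated for any imaging outcome

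*Combined protocol and SAP*

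**What the plan says.** Two places give two scans:

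- Section 9.3.1, the statistical section's statement of the imaging schedule: "Each participant will be imaged two times: upon enrollment (visit 1) and after completion of the 10 week exercise program (visit 3".
- Section 12.3, on payment: "for undergoing each MRI scan (two in total".

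Three places give three:

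- Section 1.2: "We will acquire multinuclear-MRI data at three time points: 1) baseline, 2) pre-intervention and 3) post-intervention".
- Section 3.1: "Multinuclear-MRI data will be acquired at baseline, as well as before and after the intervention".
- Attachment A marks MRI at Weeks 1, 5 and 18.

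The primary objective in 9.1 is to "assess and compare the interventions (exercise versus control phase in the same individual", for outcomes that include DTI, 31P-MRI, BOLD-MRI and IDEAL-MRI; 2.1 states the same objective. By 3.1, all participants have a 4-week period without exercise and then the 10-week programme, in that order.

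The analysis sections do not agree with each other. Section 9.3 models change with a binary indicator of intervention, 9.3.4 gives the control phase a weight of 1, and 9.4 powers an exercise-control difference for BOLD and PCr. Section 9.3.2 compares baseline with follow-up and has no control term, and 9.3.5 says that groups will not be compared.

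On timing, the Protocol Summary gives participant duration as about 10 weeks, and 4.5 says: "Participants will be enrolled for a minimum of 10 weeks". Section 4.7.2 refers to a post-non-exercise visit in 6.4.3, and the table of contents lists one, but the body of section 6 does not describe it.

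**The concern.** There is one group and the order of phases is fixed, so the non-exercise phase is the only comparator. A control-phase change needs a measurement at the end of that phase and before exercise begins. This is the scan that 9.3.1 leaves out.

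The omission does not look like an isolated slip. Section 12.3 repeats the count of two, and 9.3.2 and 9.3.5 read naturally as a pre-post study on two scans. Someone running the study or the analysis from section 9 could leave the middle scan out and see no conflict with the sections next to it. Once a participant has started to exercise, that scan cannot be recovered.

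**Working it through.** **1. The plan's own figure.** Section 9.4 states more than 80% power for the exercise-control difference, for BOLD and PCr only. The inputs are N = 40, two-sided alpha 0.05, and the Table 4 changes (mean, SD): BOLD 1.11, 1.26 with exercise and 0.18, 1.42 with control; PCr 10.61, 12.85 and 0.06, 8.53.

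Power = Φ(d / (s√(2/n)) − 1.96), with s = √((s_E² + s_C²)/2).

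- BOLD: d = 1.11 − 0.18 = 0.93; s = √((1.5876 + 2.0164)/2) = 1.342; d/SE = 0.93/0.300 = 3.10; power 0.87 (0.86 by noncentral t).
- PCr: d = 10.61 − 0.06 = 10.55; s = √((165.12 + 72.76)/2) = 10.91; d/SE = 10.55/2.439 = 4.33; power 0.99.

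The statement reproduces, but it takes 40 control changes and 40 exercise changes. The detectable differences are close without being exact. For BOLD, 2.80 × 0.300 = 0.841, which is 4.67 times the control change (stated 4.5). For PCr, 2.80 × 2.439 = 6.83, which is 114 times (stated 120). The plan labels these ratios as percentages; they are multiples of the control change (0.93/0.18 = 5.17; 10.55/0.06 = 175.8).

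**2. Two scans.** Let Y1, Y2 and Y3 be the outcome at enrolment, at the end of the non-exercise phase and after exercise.

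- Control change C = Y2 − Y1; exercise change E = Y3 − Y2.
- Target: E − C = Y3 − 2Y2 + Y1.
- Available under 9.3.1: Y3 − Y1 = E + C.

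The sum of the two changes is observed and their difference is not. The intervention indicator in 9.3 has one level, and the control-phase weight in 9.3.4 has nothing to weight. Of 40 participants, 0 have a control-phase MRI change, so the power in step 1 is undefined. The study would take 40 × 2 = 80 scans, against 40 × 3 = 120 on the other schedule.

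As an illustration, suppose the Table 4 means held for the two phases here (an assumption). The two-scan BOLD change would have expectation 1.11 + 0.18 = 1.29, where the controlled difference is 0.93. For PCr the figures are 10.67 and 10.55.

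**3. Intervals in Attachment A.** MRI at Weeks 1, 5 and 18 gives a control interval of 4 weeks and an exercise interval of 13 weeks, the latter containing the 10 exercise weeks (Weeks 7 to 16). The two-scan interval is 18 − 1 = 17 weeks.

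**4. Three scans.** E − C is now estimable, with 40 changes per phase, but C and E share Y2. With equal variance σ² and the same correlation ρ between any two scans:

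- Cov(C, E) = σ²(ρ − 1 − ρ + ρ) = −(1 − ρ)σ²
- Var(C) = Var(E) = 2(1 − ρ)σ²
- Corr(C, E) = −0.5

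Paired t-test on E − C with SD = √(s_E² + s_C² − 2r·s_E·s_C):

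- BOLD, r = −0.5: SD = √(3.604 + 1.789) = 2.322; power 0.69.
- PCr, r = −0.5: SD = √(237.88 + 109.61) = 18.64; power 0.94.
- For r from −0.5 to +0.5: BOLD 0.69 to 0.99, PCr 0.94 to above 0.99.

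The Table 4 SDs differ between exercise and control, so equal variances can hold only approximately. The documents give no correlation between successive changes.

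**The case against.** The best defence is that three scans are plainly intended. The rationale, the design section and the schedule all say so, and calling the last scan visit 3 implies a visit 2. On that view 9.3.1 and 12.3 are stale wording. This is probably right, and it limits the point: the documents contradict themselves on the scan count, and they do not establish a two-scan design. It does not remove the point, because section 9 is where an analyst will look.

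A second defence is that 9.3.2, the section on the primary efficacy endpoints, can be run on two scans, and that the hypotheses in 9.2 mention no control. Both statements are correct. A reader might infer that the MRI hypotheses all become untestable, but as worded they do not. What fails is the comparison in 2.1, 9.1, 9.3 and 9.4.

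Two other inferences go too far:

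- *That 4.5 excludes a 4 + 10 week course.* It sets a minimum and expects some participants to stay longer. Only the summary's figure of about 10 weeks conflicts, although 4.5 explains longer stays by scheduling and never mentions the non-exercise phase.
- *That the middle scan rests on Attachment A alone, and so could be dropped without an amendment.* Of the attachments the plan does say: "These documents are relevant to the protocol, but they are not considered part of the protocol". But 1.2 and 3.1 commit to the scan in the body and 4.7.2 relies on the visit, so dropping it would contradict the protocol itself. What section 6 lacks is a description of the visit.

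**Conclusion.** The contradiction stands and needs to be corrected. The consequence is conditional: if 9.3.1 governs, no imaging outcome has a control-phase change, exercise versus control is not estimable for DTI, 31P, BOLD or IDEAL, and the only MRI change mixes the non-exercise phase into the exercise effect. If 1.2, 3.1 and Attachment A govern, the comparison can be made. It would be wrong to conclude that the trial cannot address its primary objective on imaging.

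Correcting the count is not enough alone. Sections 9.3.2 and 9.3.5 would still describe an analysis with no control term. The power claim in 9.4 reproduces only when the two changes are treated as independent; with the shared scan, BOLD power is about 0.69 under equal variances and ρ = 0.5 at all three scans, while PCr stays above 0.9.

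The third scan also does nothing for non-imaging outcomes. Attachment A marks MNSI at Weeks 0, 1 and 18 and bloodwork at Weeks 1 and 18, so neither has an end-of-control measurement. That is a separate matter.

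**What to change.** - **9.3.1 and 12.3:** state three scans: baseline, end of the non-exercise phase, and post-exercise. Define control change as scan 2 minus scan 1, and exercise change as scan 3 minus scan 2.
- **Section 6:** restore the post-non-exercise visit, with its MRI, and align the numbering with 4.7.2 and the table of contents.
- **Protocol Summary and 4.5:** correct the duration of about 10 weeks, and state in 4.5 that participation includes the 4-week phase.
- **9.3.2 and 9.3.5:** reconcile with 9.1 and 9.3, so that the primary analysis contains the phase comparison, or state explicitly which analysis answers the primary objective.
- **9.4:** recheck power for the exercise-control difference with the shared scan, over a stated range of correlations.

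The cost is amendment wording and a short power recalculation. If only two scans were budgeted, add 40 × $50 = $2,000 in participant payments, travel of up to 40 × $20 = $800 at the rate in 1.2, and scanner time for 40 sessions. The documents do not price scanner time, and 4.5 notes that scanner availability is limited. The scan itself is already required by 1.2, 3.1 and Attachment A.
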